8.3.3. Timing of Initiation of Intervention

The intervention is to begin on the day following the evaluation of the eligible and consented subject at the pre-operative clinic/surgeon's office. Daily oral doses will continue through the hospital admission for elective surgery. For patients without side effects, dosing will continue daily for 90 days after the surgical encounter.

Patients will be contacted between the pre-operative clinic/surgeon's office visit and surgery to evaluate study drug compliance as well as any adverse events associated with the study drug.

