### 9.1. Primary Endpoint

The primary endpoint for this domain is the REMAP primary outcome of hospital free days at 90 days after the index date (HFD-90). The index date for HFD-90 outcome is defined as the date of the elective surgical encounter.

Hospital free days Score	Score
-1	Patient died during surgery or within the 90 days following their surgical intervention
0	No days out of the hospital in the 90 days following the surgical intervention
1-90	One to 90 days out of the hospital and alive in the 90 days following the surgical intervention

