### 9.2. Secondary Endpoints

Secondary domain-specific outcome measures include information about EHR based alerts reported during the index elective surgical admission, perioperative outcomes, and surgical outcomes.

Specifically, they include:

- Perioperative outcomes (enrollment to postoperative 90 days)
  - Gastrointestinal intolerance (dichotomous; present/absent)
  - SAE as defined in Core Protocol (mild, moderate, severe, life threatening/disabling; adjudicated as related, possibly related, unrelated)

- Surgical outcomes
  - Index admission
    - Postoperative intensive care unit (ICU) admission (dichotomous; any admission/none)
    - ICU length of stay (LOS; continuous, days)
    - Hospital LOS (continuous, days)
    - Discharge disposition (categorical; Home, SNF/LTAC, Death/Hospice)
    - In-hospital mortality (dichotomous; yes/no)
  - 30-day outcomes
    - Organ failure free days (i.e., vasopressor exposure, hemodialysis, or mechanical ventilation; continuous, days)
    - Surgical site infection, as defined by NSQIP and the CDC (categorical)
    - Surgical site occurrence, as defined by Ventral Hernia Working Group (categorical)
  - 90-day outcomes
    - Reoperation/reintervention, both incidence and total number (dichotomous, time to event; any/none and continuous, number)
    - Readmission (dichotomous, time to event; any/none, days)
    - Venous thromboembolic events including deep vein thrombosis and pulmonary embolus after surgery (dichotomous, time to event; any/none, days)
    - Mortality (dichotomous, time to event; yes/no, days)

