## 10. GRAPHICAL DATA SUMMARIES

1. Overall cohort accrual, including number of subjects screened, number excluded for each inclusion/exclusion criteria, and number of subjects per preoperative enrollment category will be presented graphically as a flow/consort diagram.
2. All ordinal endpoints will be plotted using stacked cumulative bar plots and cumulative probability plots.
3. All time-to-event endpoints will be plotted using Kaplan-Meier plots. Positive clinical event outcomes will be plotted as the cumulative rate of event, and negative events will be plotted as the cumulative rate of event-free.
4. All continuous endpoints will be plotted using histograms and boxplots.

5. All Bayesian logistic and frequentist logistic regression models will be plotted using forest plots.

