### *Frequentist Sensitivity Analyses*

In addition, sensitivity analyses will be conducted in which frequentist regression models are used in place of the Bayesian cumulative logistic regression and without borrowing across groups. For these analyses, we will assess HFD-90 by 4 definitions of treatment arms based on the intervention, on both the ITT and PPA populations:

1. Treated (any duration and/or dose combined to a single group) vs. placebo
2. Metformin 1500mg ER vs. Metformin 1000mg ER vs. Metformin 500mg ER vs. Placebo (each pooled across duration)
3. Long Metformin (>90 days) vs. Medium Metformin (29-90 days) vs. Short Metformin (7-28 days) vs. Placebo (each pooled across the 3 doses of study drug)
4. Placebo vs. 500mg and 7-28 day duration vs. all other treatment combinations

For each of these definitions, we will apply two approaches:

1. A frequentist proportional odds model for the cumulative odds of 90-day HFD being less than or equal to a cut point  $c$ , where  $c = -1, \dots, 89$ , as described in the primary Bayesian analysis above. The treatment effect will be estimated, adjusting for surgical strata and duration as covariates.
2. A Mann-Whitney U test with ties for differences in HFD-90 by treatment arm. Test statistics and p-values will be presented. We will report death as a dichotomous outcome (vs. no death) and, among survivors, HFD-90 as a continuous outcome, as outlined in Section 11.

In the logistic regression model, the model structure will be as follows:

$$y_i = \text{logit}(\beta_0 + \beta_i * \text{tx arm}_i + \varepsilon_i);$$

Where:

$y_i$ : Outcome (HFD-90 = 90 vs.  $\neq 90$ ) for subject i

$\beta_0$  = Coefficient for intercept (for odds of outcome for placebo (reference) group)

$\beta_i$  = Coefficient(s) for treatment(s) vs. placebo

$\varepsilon_i$  = Residual Error for Subject I (i.e. Subject-level random/residual error)

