### **13.3. Subgroup Analyses**

For the primary outcome of HFD-90 only, subgroups will be evaluated using a frequentist cumulative logistic regression model, as in the primary analysis. These analyses will be conducted on both the ITT and PPA populations and will follow the same approach to pooling across duration and borrowing across dose as in the primary analysis. Analyses will be stratified by each of the following subgroups:

1. Age >= overall median vs < overall median (hypothesis, more effective among those > median)
2. Sex at birth (hypothesis: no difference)
3. Frailty, comparing robust/normal vs. frail/very frail (hypothesis, more effective among frail and very frail). Note that subgroup of robust with normal and frail with very frail may be modified as necessary (e.g., to robust vs. normal/frail/very frail) if sample size for either group is <= 25).
4. Surgical strata (hypothesis, no difference)
  - o No operation
  - o Spine
  - o General surgery/surgical oncology
  - o Colorectal Surgery
  - o Other
  - o Any strata with <= 25 subjects will be combined into the "Other" category, except the "No operation" group
5. Surgical stress (hypothesis, more effective among higher stress procedures)
  - o Same day surgery procedures
  - o Procedures with subsequent hospital admission

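### As worded, the surgical-stress subgroup in SAP 13.3 sorts patients by hospital admission after surgery, which follows randomisation and is itself part of HFD-90

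*SAP*

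**What the plan says.** SAP 13.3 lists five subgroups for HFD-90. The fifth, surgical stress, carries the hypothesis of a larger effect in higher-stress procedures. Its levels are same-day procedures and "Procedures with subsequent hospital admission". Nothing says that the level is fixed at scheduling or at randomisation.

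Protocol 8.3.3 puts the start of study drug before surgery: "The intervention is to begin on the day following the evaluation of the eligible and consented subject". SAP 6 gives a shortest pre-operative exposure of 7 days. SAP 9.1 starts HFD-90 at the date of surgery and scores survivors with time at home as "One to 90 days out of the hospital and alive in the 90 days following the surgical intervention". Among the index-admission outcomes in SAP 9.2 is "Hospital LOS (continuous, days)".

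On method, SAP 13.3 says: "Analyses will be stratified by each of the following subgroups". The model is frequentist, yet the analyses "will follow the same approach to pooling across duration and borrowing across dose as in the primary analysis".

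**The concern.** Whether a patient is admitted after surgery is settled after randomisation and after days or weeks of study drug, and each index inpatient day reduces HFD-90. Splitting on it means conditioning on part of the endpoint. If metformin changes who is admitted, the patients left in each level differ between arms, and the OR within a level no longer compares randomised groups.

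A second consequence needs no drug effect. A level defined by no admission scores 90 unless the patient is readmitted or dies, so it cannot show a benefit on the index stay. The hypothesis about higher-stress procedures is then tested unevenly by construction. A reader could take the resulting contrast for effect modification.

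**Working it through.** The plan states no expected estimate or power for its subgroups, so there is no figure to reproduce. The steps below size the problem.

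**Inputs from the documents.** OR 0.8, the clinically significant difference in Protocol 10.1. Allocation √3:1:1:1 (SAP 6), so the placebo share is q = √3/(√3+3) = 0.366. The trial stopped before the 500-patient analysis (SAP 4), so 499 is taken as the upper limit.

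**Assumed, because the documents give no values.** Placebo admission p of 30 to 85%; index stay lognormal with median 3 days and sigma 0.8; where used, readmission of 10% (admitted) and 4% (same-day) and death of 2% and 0.5%; 200 patients as a lower size. Same-day discharge is scored 90.

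**1. Uniform OR 0.8, no readmission or death.** Admitted then means HFD-90 of 89 or less. Let a be the placebo probability of HFD-90 ≤ c.
- Treated probability: 0.8a/(1 − 0.2a). Treated admission: 0.8p/(1 − 0.2p).
- Odds among the admitted: a/(p − a) on placebo and a(1 − 0.2p)/(p − a) on metformin.
- OR among the admitted = 1 − 0.2p at every cutpoint: 0.94, 0.90, 0.86 and 0.83 at p = 30, 50, 70 and 85%. At 95% it is 0.81.
- Same-day patients all score 90 and give no estimate.

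**2. Only the shortest stays are averted, admission OR 0.8.** Longer stays are unchanged in number, so a is equal in both arms and the OR among the admitted is (p − a)/(p_T − a), where p_T is treated admission. This exceeds 1.
- p = 30%: p_T = 0.24/0.94 = 0.255. At a = 0.15 the OR is 0.15/0.105 = 1.42. A proportional odds fit over all cutpoints gives 1.56 (1.41 to 1.58 over the stay distributions tried), against 0.85 in the full population.
- p = 85%: the fit gives 1.10 among the admitted and 0.97 overall. At 95% the admitted OR is 1.03.

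**3. No drug effect.** All ORs are 1.00.

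**4. Planned setting as the split.** Readmission and death are included. Planned inpatients are admitted in 80 to 98% of cases and planned same-day patients in 5 to 40%. The ratio of ORs between levels should be near 1, because the effect on stay is uniform.
- Drug acts on the index stay only: 0.83 to 0.90 with the split as worded, 0.91 to 1.01 with planned setting.
- Drug also lowers readmission (OR 0.8): 0.97 to 1.05 as worded, 0.98 to 1.00 planned.

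**5. The ceiling.** With 4% readmission and 0.5% death, 4.5% of an actual same-day group score below 90: about 11 of 250 patients, or 4 to 5 of 100. If 5% of planned same-day patients are admitted, the share is 0.05 + 0.95 × 0.045 = 9%.

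**6. Precision.** Per level, var(log OR) = 3v/[n × I], with v = 1/[q(1 − q)] = 4.31 for pooled metformin and I = 1 − Σπ³, where π are the outcome category proportions. I is 0.95 at best, about 0.13 for actual same-day patients (1 − 0.955³) and 0.25 for planned same-day patients at 5% admitted. With a half-and-half split, the SE of the log ratio of ORs, and the 95% limits as a factor either side, are:
- split as worded: 0.68 (factor 3.8) at 499 patients, 1.07 (8.1) at 200;
- planned setting, 5% of same-day patients admitted: 0.51 (2.7) and 0.80 (4.8);
- best case: 0.33 (1.9) and 0.52 (2.8).

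Ratios of 0.83 to 0.90 are |ln| = 0.19 to 0.11, or 0.2 to 0.3 of an SE of 0.68. Step 2 at p = 30% gives ln 1.56 = 0.44, about 0.7 of the contrast's SE (0.61 at that admission rate). Read alone, that admitted-group OR is nearly 1.5 of its own SE (0.31, about 136 patients), still inside the 95% limits.

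**The case against.** The strongest reply concerns intent. Both levels and the hypothesis speak of procedures, which fits a classification of operations rather than of what happened to each patient. That reading is possible, but no section states it. A reader might infer that the sponsor meant to use actual admission; the documents do not establish that either.

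The size is also limited. Every magnitude rests on assumed rates, and the distortion needs a drug effect on admission. Protocol 8.1 describes patients admitted to UPMC facilities, and at 85 to 95% admission step 1 gives 0.83 to 0.81 and step 2 gives 1.10 to 1.03. The most striking figure, 1.56, needs 30% admission and a drug that averts only the shortest stays. This is one of five subgroups in a trial that stopped early. All of this stands and limits the weight of the point. It does not make the worded split a sound one.

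Three stronger readings are tempting and not supported.
- A reader might infer that the borrowing instruction in SAP 13.3 contradicts the frequentist sensitivity section, which describes analyses "in which frequentist regression models are used in place of the Bayesian cumulative logistic regression and without borrowing across groups". That sentence covers only those sensitivity analyses. The mismatch lies within 13.3 and against SAP 13.1, where borrowing comes only from a hierarchical Bayesian prior.
- A reader might infer that the lack of a between-level estimate biases the subgroups. It is a reporting gap: stratified fits are planned, SAP 10 adds "All Bayesian logistic and frequentist logistic regression models will be plotted using forest plots", and a ratio can be derived from them.
- A reader might infer that planned setting cures the ceiling. It raises the share scoring below 90 from about 4.5% to 9% in the example, no more.

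**Conclusion.** The point holds for the surgical-stress subgroup as worded. The split is made after randomisation on a component of HFD-90. If metformin affects admission, the within-level ORs can be diluted (0.94 to 0.83 where the true OR is 0.8) or reversed among admitted patients. If it does not, there is no distortion, though same-day patients still cannot show an index-stay benefit.

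These sizes rest on assumed admission, stay, readmission and death rates. At no more than 499 patients, the distortion of the contrast between levels is smaller than its SE in the cases worked here. The primary analysis and the age, sex and frailty subgroups are not touched. The reason to act is that a larger sample would not cure the problem and the correction is cheap. The borrowing wording and the missing contrast are secondary.

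**What to change.** Before unblinding, define surgical stress by planned same-day against planned inpatient setting or, if planned setting was not recorded, by scheduled procedure type. Fix the class as it stood before surgery, abstract it blind to arm, and keep actual admission as an outcome only. If planned setting was the intent, one sentence in SAP 13.3 is enough.

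The cost is wording and some chart abstraction; SAP 11 already draws on the electronic health record. The documents do not say whether planned setting is held there, so the procedure classes for the fallback should be listed in advance. No patients or procedures are added. The ceiling in same-day patients is eased, not removed, and the contrast stays imprecise.

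Optional:
- For age, frailty and surgical stress, report the ratio of ORs between levels with a 95% interval, labelled exploratory. It follows from the planned fits as a difference of log ORs with variances added.
- Reconcile the model wording in 13.3. Either drop the borrowing across dose and use a frequentist proportional odds model with dose arms pooled across duration (no duration covariate, and no stratum covariate within the surgical-strata subgroups), or use the Bayesian primary model within subgroups.

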### **13.4. Exploratory Analyses**

Exploratory analyses after unblinding will not be considered inferential. Any *post hoc* exploratory analyses will be clearly labeled as exploratory and will use the conventions below.

1. Ordinal endpoints will be compared using a cumulative proportional odds model with summaries of the OR, 95% credible intervals, and Wilcoxon tests for robustness against a lack of proportional odds.
2. Time-to-Event analyses will utilize a Cox proportional hazards model, summarizing the hazard ratios and 95% confidence intervals.
3. Continuous endpoints will compare means with 95% confidence intervals based on two-sample t-test and/or Mann Whitney U test procedures.
4. Dichotomous proportions will be compared using logistic regression summarizing the OR and 95% confidence intervals. Differences between proportions will be summarized using observed differences and normal approximations for the 95% credible intervals.

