## **6. INTERVENTIONS**

There is one active intervention and one control within this analysis plan:

- 1- Metformin
- 2- Placebo

Preoperative duration of study drug was pragmatically chosen based upon the time interval between the time of enrollment and scheduled operating room date including:

- 1- Short – 7-28 days
- 2- Medium – 29-90 days
- 3- Long – >90 days

Preoperative duration is not considered in the primary model but was considered in planned sensitivity analyses. Patients were randomly assigned,  $\sqrt{3}$ :1:1:1 to placebo and the 3 doses of metformin:

- 1- Placebo
- 2- Metformin 500mg ER
- 3- Metformin 1000mg ER
- 4- Metformin 1500mg ER

The dosing of and route of administration of metformin guidance included to take an oral dose once daily and complete all dispensed medication from the provided pill bottle.

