## 13. ANALYTIC APPROACH

Primary inferential analyses will be done using a Bayesian approach. Sensitivity analyses will be conducted using both Bayesian and Frequentist approaches, as described. Secondary endpoints will be analyzed using frequentist approaches. A summary of the analyses methods is provided below. For all frequentist models, statistical significance will be defined as a one-sided p-value of <0.025, and for all Bayesian models a one-sided posterior probability > 0.975. If stable inference cannot be made due to sparseness of data within strata/categories, data may be further collapsed as needed.

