## 13.2. Analytic Approach for Secondary Endpoints

### *Primary Analysis*

The analysis of secondary endpoints will be conducted with Frequentist methods using unadjusted linear regression, logistic regression, and Cox models for continuous, dichotomous, and time-to-even secondary endpoints, respectively on both the ITT and PPA populations. Secondary endpoints are described in section 9.2 above. Treatment arms will be pooled across all durations and doses to form treated vs. placebo groups, with the placebo group used as the reference category in all analyses. There will be no adjustment for covariates, other than treatment arm.

The model structures will mimic the approach used in the frequentist analysis of the primary endpoint above. Specifically:

Linear regression:

$$y_i = \beta_0 + \beta_i * tx\_arm_i + \varepsilon_i;$$

Logistic regression:

$$y_i = \text{logit}(\beta_0 + \beta_i * tx\_arm_i + \varepsilon_i);$$

Cox Regression:

$$h(t|x_i) = h_0(t) * \exp(\beta_i * tx\_arm_i);$$

Where:

$y_i$  or  $h(t|x_i)$ : Secondary outcome of interest for subject  $i$

$\beta_0$  or  $h_0(t)$  = Coefficient for intercept or baseline hazard estimate

$\beta_i$  = Coefficient(s) for treatment(s) vs. placebo

$\varepsilon_i$  = Residual Error for Subject  $i$  (i.e. Subject-level random/residual error)

Statistical significance will be defined as an unadjusted  $p < 0.025$ . For all models, outputs will be reported using standard conventions and will include regression coefficients, standard deviations, confidence intervals, test statistics, and p-values, as relevant to each model. Model outputs will be reported both graphically and in tables, as described in sections 10 and 13.10.

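### SAP 13.4 item 4 gives post hoc risk differences a normal-approximation interval with no sparse-event rule; read as the usual Wald interval, it misstates uncertainty when few or no events occur (minor)

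*SAP*

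**What the plan says.** SAP 13.4 sets conventions for post hoc analyses and limits their weight: "Exploratory analyses after unblinding will not be considered inferential". Item 4 covers binary outcomes. It first gives a relative measure, "Dichotomous proportions will be compared using logistic regression summarizing the OR and 95% confidence intervals", and then an absolute one, "Differences between proportions will be summarized using observed differences and normal approximations for the 95% credible intervals". No prior, no posterior model and no minimum event count is given.

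The SAP gives no other method for a difference in proportions. Planned secondary endpoints are analysed under 13.2 with "unadjusted linear regression, logistic regression, and Cox models for continuous, dichotomous, and time-to-even secondary endpoints", and 13.2.1 adds counts and percentages. The one small-sample safeguard, in SAP 11, withholds modelling for interventions with fewer than 10 subjects. It counts subjects, not events, so an arm of 190 patients with no events passes it.

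**The concern.** The Wald interval estimates each arm's variance from its observed proportion. An arm with no events therefore contributes no variance, and two arms with no events give an interval of zero width. The binary outcomes in SAP 9.2 include in-hospital death, 90-day death, venous thromboembolism and reoperation. The trial stopped before its first interval analysis at 500 patients (SAP 4), so low counts are plausible.

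At stake is how a reader takes absolute benefit or harm in an exploratory table. No events in either arm would appear as a perfectly precise null. A handful of events against none would appear as an interval clear of zero. At 4 vs 0, the odds ratio in the same item cannot be estimated by maximum likelihood, so readers would lean on the difference exactly where its interval is least reliable.

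**Working it through.** **Inputs.** The plan states no coverage, event rate or final sample size, so it has no figure to reproduce.

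- Allocation √3:1:1:1 (SAP 6): placebo 1.732/4.732 = 36.6%, each dose 1/4.732 = 21.1%, pooled metformin 63.4%.
- Total N: not given. Assumed 100 to 500, with 500 as the upper edge because the trial stopped before that look.
- Rare-event rates: not given. Assumed 1% and 2%.

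**Formula.** Wald: d ± 1.96 √[p₁(1−p₁)/n₁ + p₂(1−p₂)/n₂], where d = p₁ − p₂.

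**Four events against none (N = 300: 190 metformin, 110 placebo).** p₁ = 4/190 = 0.02105 and p₂ = 0. SE = √(0.02105 × 0.97895/190) = 0.01041. The interval is 0.02105 ± 0.02041, or 0.06 to 4.15 points.

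Fisher's exact test conditions on 4 events in total:
- P(all 4 on metformin) = (190·189·188·187)/(300·299·298·297) = 0.159
- P(1 on metformin) = 0.124
- P(0 on metformin) = 0.017
- Two-sided p = 0.159 + 0.124 + 0.017 = 0.300

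On the same data Newcombe gives −1.5 to 5.3 points and Agresti-Caffo −1.1 to 4.6.

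This does not depend on N. With x events of n in one arm and none in the other, Wald excludes zero when x > 1.96²(1 − x/n) = 3.84(1 − x/n). Four events always satisfy this. With four on pooled metformin and none on placebo, Fisher's p is 0.29 at N = 100 and 0.30 at N = 499. The reverse pooled pattern (0 metformin, 4 placebo) has p of about 0.02, so there is no conflict there.

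**No events in either arm.** Both variance terms are 0, so Wald is 0 to 0 at any N. Newcombe for 0/190 vs 0/110 is −3.4 to 2.0 points.

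**Coverage.** Binomial probabilities are summed over every pair of counts whose Wald interval contains the true difference (nominal 95%).

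| N | Pooled arms | Metformin 1%, placebo 2% | Metformin 2%, placebo 1% | Dose/placebo arms | Dose 1%, placebo 2% | Dose 2%, placebo 1% |
|---|---|---|---|---|---|---|
| 100 | 63/37 | 73.6% | 79.9% | 21/37 | 61.5% | 54.4% |
| 200 | 127/73 | 76.6% | 93.8% | 42/73 | 83.8% | 77.8% |
| 300 | 190/110 | 88.3% | 94.5% | 63/110 | 92.6% | 71.6% |
| 500 | 317/183 | 92.5% | 94.9% | 106/183 | 94.5% | 87.5% |

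In these cells Newcombe covers at least 96% and Agresti-Caffo at least 97%. The 54.4% is mostly the zero-width case: P(no events) = 0.98²¹ × 0.99³⁷ = 0.45, and each such result misses the true 1-point difference.

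**No true difference, 1% in both pooled arms.** Zero is excluded 0.3% of the time at N = 100, 2.1% at 200, 4.5% at 300 and 7.0% at 500. The last splits into 6.4% towards more events on metformin and 0.7% towards fewer (rounded), against a nominal 2.5% each side. The smaller placebo arm is more often empty: at N = 500, 0.99¹⁸³ = 16% against 0.99³¹⁷ = 4%.

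**Common events.** For pooled arms with rates of 10% or 30% in both, or 40% vs 20%, coverage is 93–95%.

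**The case against.** Four points can be made for the plan.

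1. **Scope.** A reader might infer that the planned error bars for death, thromboembolism or reoperation are wrong. The documents do not support that. Those endpoints go through logistic or Cox regression under 13.2, and neither 13.2 nor 13.2.1 calls for a risk difference. The interval arises only in a post hoc analysis labelled as exploratory. This stands and caps the severity.

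2. **Unknown N and rates.** A reader might also infer that coverage is known to be far too low for this trial's events. It is not. Protocol 11.2 calls adverse events rare, but it is describing the drug's toxicity and gives no figure; it says nothing on surgical death or thromboembolism. Protocol 6.2.3 cites 30–60% for gastrointestinal discomfort, where the approximation works. Pooled coverage near N = 500 is close to nominal. The shortfall is conditional. The 4-vs-0 and 0-vs-0 behaviour is not.

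3. **Wording.** A normal approximation to a posterior is an ordinary meaning of the text. With Beta(1,1) priors (an assumption), 4/190 vs 0/110 gives posterior means 5/192 and 1/112 and an interval of −1.13 to 4.55 points, which includes zero. 0 vs 0 gives −2.4 to 1.6. On that reading the problem disappears. But the SAP states no prior and pairs the term with frequentist logistic regression. Two tenable readings that disagree on the same data are a reason to specify.

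4. **Choice of replacement.** Insisting on Newcombe alone would be preference, since Agresti-Caffo performs comparably. This stands.

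**Conclusion.** The point holds as a minor one, limited to post hoc differences in proportions with sparse events. Under the plug-in reading two failures need no assumption about rates: a zero-width interval at 0 vs 0, and exclusion of zero at four events on pooled metformin against none on placebo, where Fisher's p is about 0.30. Under-coverage of about 54–88% needs the assumed unequal rates of 1% and 2%, together with either a small N or the less favourable direction of a single-dose comparison. For pooled arms near N = 500 it shrinks to about 93–95%.

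The excess of false exclusions towards harm should not be read as a general property. It belongs to the pooled comparison, where placebo is the smaller arm, and at 1% in both arms total exclusions are below 5% up to N = 300. No primary or planned secondary conclusion changes.

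**What to change.** In SAP 13.4 item 4, replace the normal approximation with one named method that behaves well at zero counts. Either use a 95% confidence interval for the difference (Newcombe hybrid Wilson, or Agresti-Caffo), or, if a credible interval is meant, use the equal-tailed 95% interval for the difference of two independent Beta posteriors with the prior stated, for example Beta(0.5, 0.5). Make the label match the method, and apply the same method to any risk difference reported.

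The cost is one sentence and one software option. Intervals for rare events become slightly wider and mildly conservative; for common events they barely change.
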